### 3.4 Justification of the Dose

[figure not shown]
The clinical dose regimen was selected based on biodistribution and dosimetry data from a subset of patients with neuroendocrine tumours, belonging to the same group of 140 patients of the Bad Berka retrospective study treated with  $^{177}\text{Lu}$ -edotreotide (Schuchardt et al., 2013; van Echteld et al., 2014; Baum et al., 2016), supported by detailed pharmacokinetics and biodistribution data of  $^{86}\text{Y}$ -edotreotide from Novartis Phase I clinical studies (Jamar et al., 2003; Barone et al., 2005). Furthermore the recommendations of the joint IAEA, EANM, and SNMMI practical guidance on peptide receptor radionuclide therapy (PRRNT) in neuroendocrine tumours (Zaknun et al., 2013) have been taken into consideration.

The detailed examination of the pharmacokinetics and biodistribution of therapeutic radiolabelled edotreotide was performed in a Phase I, single-centre, open label, cross-over study of 24 GEP-NET patients (Jamar et al., 2003) and in a subset of 18 GEP-NET patients enrolled in a Phase-I multicentre study (Barone et al., 2005), using the positron emitting isotope yttrium-86 ( $^{86}\text{Y}$ ) and the inherent quantitative advantages of positron emission tomography (PET) imaging.  $^{86}\text{Y}$ -edotreotide is an appropriate surrogate to quantitatively predict the in vivo behaviour of the therapeutic compound, not only radiolabelled with chemically identical  $^{90}\text{Y}$ , but also when radiolabelled with chemically very similar  $^{177}\text{Lu}$ . Since Y(III) and Lu(III) belong to the same group of trivalent rare-earth elements with very similar chemical properties, Y(III) and Lu(III) reveal almost identical nine-coordinate structure and thermodynamic stability of the complexes with DOTA-chelator (Viola-Villegas & Doyle, 2009). Furthermore, the  $^{86}\text{Y}$  half-life of 14.74 h allows quantitative PET investigations up to 48 h p.i., which is adequate for the pharmacokinetics and biodistribution analysis of therapeutic  $^{90}\text{Y}$ - and  $^{177}\text{Lu}$ -edotreotide.

The main outcome of the Novartis Phase-I pharmacokinetics and biodistribution studies was a large variability in individual renal uptake. Kidney uptake and retention of  $^{86}\text{Y}$ -edotreotide varied between patients by a factor of 3 and indicated a wide range of absorbed doses during therapies, whereas body surface area only ranged between 1.50 and 2.06 m^2. Given the known safety profile and dose limiting renal toxicity, the dosing of the therapeutic agent has been proposed based on the individualised dosimetry approach (Barone et al., 2005), rather than based on body mass.

The same observation was reported in 59 patients treated with  $^{177}\text{Lu}$ -edotreotide and undergoing dosimetric evaluation by means of SPECT (Schuchardt et al., 2013). The mean kidney absorbed dose was 0.6 with a wide variation in range 0.3 – 1.6 mGy/MBq.

Figure 1 shows a selection of 19 patients from the Bad Berka dosimetry data base, who received  $7.5 \pm 0.4$  GBq  $^{177}\text{Lu}$ -edotreotide ( $= 7.5 \text{ GBq} \pm 5\%$ ). These patients belong to the same group of 140 patients of the above mentioned retrospective study. Similar to the results reported from Novartis Phase-I clinical trials, these data serve to support fixed dosing as opposed to body weight-guided dosing, since no correlation whatsoever is found between kidney absorbed dose and body weight for the same administered  $^{177}\text{Lu}$ -edotreotide dose. Furthermore, these data also serve to emphasise the importance of individual dosimetry-guided dosing, since we observe a 3-fold variation in absorbed kidney dose for the same administered  $^{177}\text{Lu}$ -edotreotide dose.

**Figure 1: Absorbed kidney dose from  $7.5 \pm 0.4$  GBq  $^{177}\text{Lu}$ -edotreotide (Schuchhardt et al., 2013)**

In summary, the selected  $^{177}\text{Lu}$ -edotreotide dosing is a regime of up to four cycles of a fixed 7.5 GBq dose per cycle, based on individual dosimetry not to exceed a 23 Gy cumulative renal absorbed radiation dose or maximally 29 Gy, provided that additional measurements of renal function ( $^{99\text{m}}\text{Tc}$ -MAG3 renal scintigraphy) are >50% of baseline. In addition, this clinical dose regimen is in line with the recommendations from recent literature and based on leading experts' opinions of joint IAEA, EANM, and SNMMI practical guidance on peptide receptor radionuclide therapy (PRRNT) in neuroendocrine tumours (Zaknun et al., 2013).

### 3.5 Protocol Adherence

Strict adherence to all specifications laid down in this protocol is required for all aspects of the study conduct; the investigator may not modify or alter the procedures described in this protocol. If protocol modifications are necessary, all alterations that are substantial and not solely of an administrative nature require a formal protocol amendment which has to be approved by the Institutional Ethics Committee(s) IEC(s) / Institutional Review Board(s) IRB(s) and Competent Regulatory Agencies/Authorities according to national regulations before the amendments can be implemented and the study may continue (see Section 13.1 for the role of IECs / IRBs and Competent Regulatory Agencies/Authorities).

If an investigator has deviated from the protocol in order to eliminate an immediate hazard to patients or for other inevitable medical reasons, the investigator shall document all such deviations, including the reasons thereof, and submit the document to the sponsor, the IEC(s) / IRB(s) and the relevant Competent Regulatory Agencies/Authorities if applicable, and according to national regulations.

As an exception only during the COVID-19 pandemic, the Sponsor acknowledges that some organisational and/or logistical adjustments might be necessary at the investigational sites. Deviations from this protocol that might arise in case of exceptional circumstances must be documented and

discussed with the Sponsor without delay. Every effort should be made to ensure the continuity of this study as per this study protocol and to avoid delays, treatment discontinuation, missing assessments, and study dropout.

### 3.6 Sub-studies (Lu-Edotreotide patients only)

To obtain additional exploratory data, three sub-studies will be performed at selected sites with adequate technical capabilities. Patients will be informed about sub-studies during the informed consent process (see Section 13.2). Participation requires additional consent for each sub-study.

#### 3.6.1 Sub-study A: Repetitive Full Dosimetry Imaging (D1 – D4)

The total absorbed doses (AD) to kidneys and tumour from four cycles of Lu-edotreotide (D1 - D4) will be estimated, by linear extrapolation of the AD measured on D1 with  $7.5 \pm 0.7$  GBq to the full dose of 30 GBq. Dosimetry will be measured, using serial planar and single time point SPECT imaging (see Section 8.2.2). To verify the accuracy of total AD estimations, based on a linear extrapolation of AD measured during D1, full dosimetric imaging will be repeated during subsequent cycles (D2 – D4) in a subgroup of approximately 20 patients, ready and able to undergo repetitive dosimetric imaging. For further details please refer to Clinical Imaging Manual.

#### 3.6.2 Sub-study B: 3D Dosimetry SPECT/CT Imaging

Traditionally, dosimetry imaging has been performed using serial planar scintigraphic imaging only (2D), which is still considered the standard reference methodology by regulatory authorities. Clinically, though, the combination of serial planar with single time point SPECT imaging (2D/3D hybrid imaging) has emerged as new standard with improved spatial resolution. Especially in the abdomen, where the superposition of critical organs (e.g. kidneys, intestine, liver) renders the anatomic attribution of activity to individual organs difficult, 2D/3D dosimetry has been found to be superior to 2D dosimetry.

Full 3D dosimetry (3D), is based on serial SPECT/CT imaging only, which is quantitatively reconstructed yielding activity distributions of Bq/mL in the field of view (FOV). Serial planar imaging to capture the total administered and organ bound activities (% ID) is no longer required.

In selected sites, with SPECT/CT systems, where serial 3D imaging is clinically established, abdominal SPECT images (1-2 bed positions, covering liver, kidneys, tumour, as appropriate) will be acquired in a subgroup of approximately 20 patients, in addition to the compulsory planar images at 0.5, 6, 24, and 72 – 96 h p. i. of Lu-edotreotide. SPECT imaging will be performed after planar imaging.

AD determined by 3D dosimetry, will be analysed in comparison to AD values obtained by planar (2D) and hybrid (2D/3D) dosimetry. For further details please refer to Clinical Imaging Manual.

### 3.6.3 Sub-study C: Pharmacokinetic Urine Analysis and Bone Marrow Dosimetry

Due to the prolonged imaging procedure, patients of Sub-studies A and B cannot be included in Sub-study C. Sub-study C will be performed during any one of the four  $^{177}\text{Lu}$ -edotreotide treatment cycles (the choice of which of the four cycles to collect urine and blood samples for Sub-study C will be at the investigator's discretion).

To assess in vivo stability of  $^{177}\text{Lu}$ -edotreotide, urine will be collected from all voids beginning immediately at 0 min post-dose into 4 pooled samples in intervals from 0 min post-dose to 1 hour, and 1-6, 6-24 and 24-48 hours post-injection in a subgroup of 20 patients at selected sites only (see Section 8.2.2.4).

Urine will be analysed with gamma-counting and with radio-HPLC in order to investigate the radiochemical purity of the eliminated compound.

As the radioactivity in blood was shown to be similar to that in bone marrow (Forrer et al., 2009), bone marrow dosimetry will be assessed by measuring radioactivity in blood samples at pre-defined intervals between 0 minutes and 7 days post-infusion of  $^{177}\text{Lu}$ -edotreotide in a subgroup of 20 patients at selected sites only.

Blood samples of 1 mL, each will be drawn at a site on the lower arm below the amino acid infusion site, and opposite the arm receiving the infusion of  $^{177}\text{Lu}$ -edotreotide at 0 min, 10 min, 30 min, 1 h, 3 h, 6 h, 24 h, 48 h, 3 d, and 7 d post-injection (see Table 4, and Section 8.2.2.5). Radioactivity in the blood samples will be measured using a well-type gamma-counter.

The sampling schedule is featured in the footnotes of the flowchart in Table 1, as well as in Table 4, below: (All time points post-injection (p.i.) refer to post the start of injection.)

**Table 4: Sampling Schedule Sub-study C**

	Sampling Schedule Sub-study C ‡									
Time Post-injection	Day 0*						Day 1	Day 2	Day 3	Day 7
	0 min	10 min	30 min	1 h	3 h	6h	24±3h	48±3h	72±12h	168±12h
Urine	X †			X		X	X	X		
Blood	X	X	X	X	X	X	X	X	X	X

\* Blood samples can be taken within ± 5 minutes of the scheduled time, as long as the exact sampling times are recorded in the CRF.

† Urine will be collected from all voids beginning immediately at 0 min post-dose into 4 pooled samples in intervals from 0 min post-dose to 1 hour, and 1-6, 6-24 and 24-48 hours post-injection.

‡ Sub-study C will be performed during any one of the four  $^{177}\text{Lu}$ -edotreotide treatment cycles (the choice of which of the four cycles to collect urine and blood samples for Sub-study C will be at the investigator's discretion).

In order to facilitate the patient recruitment in the regulatory required Sub-study C, [REDACTED] at the sites participating in Sub-study C and only at those sites:

Following approval of this Study Protocol Amendment and activation of [REDACTED] by the Sponsor, the patients who consent to participate in Sub-study C and who comply with all

protocol inclusion and exclusion criteria will directly be allocated to the PRRT arm (See Section 3.1) until a global cumulative number of 20 evaluable patients is reached for the Sub-study C.

Aside from this [REDACTED] and the tests conducted for Sub-study C (see above), the treatment regimen and patient care management will remain identical to that implemented in the main study. However, [REDACTED]  
[REDACTED]  
[REDACTED]

After this [REDACTED] Sub-study C cohort is closed or if not activated or during the time this cohort is activated for the patients who consent to participate in the main study but not in the Sub-study C, the patients have the possibility to be randomised in the main study until study termination provided they comply with all protocol inclusion and exclusion criteria.

The sites not participating in the Sub-study C continue to only enroll patients using the randomization procedure of the main study.

## 4 Study Population

### 4.1 Patient Population

It is planned to randomise 300 patients with histologically confirmed well-differentiated neuroendocrine tumours of gastroenteric or pancreatic origin (GEP-NET), which have inoperable, progressive, and somatostatin receptor positive (SSTR+) disease, as evidenced by somatostatin receptor imaging (SRI). To uniformly and consistently characterise the study population according to current classification systems, a central pathologist will confirm histological diagnoses, based on historical or current tumour specimens.

To facilitate the patients recruitment in the Sub-study C, [REDACTED]  
[REDACTED] at all sites participating in the Sub-study C until 20 evaluable patients are obtained globally. [REDACTED]  
[REDACTED]  
[REDACTED]

### 4.2 Eligibility

#### 4.2.1 Inclusion Criteria

All patients must meet all of the following criteria:

1. Written informed consent
2. Male or female  $\geq 18$  years of age

3. Histologically confirmed diagnosis of well-differentiated neuroendocrine tumour of non-functional gastroenteric origin (GE-NET) or both functional or non-functional pancreatic origin (P-NET), grade G1 or G2 (Ki-67  $\leq 20\%$ ), unresectable or metastatic, in a patient who is either treatment-naïve (1st line) or who has progressed under prior therapy (2nd line)
4. Availability of existing biopsy specimen from primary tumour or metastasis or, if unavailable, willingness to undergo current biopsy for secondary central analysis
5. Measurable disease per RECIST 1.1, on CT/MRI scans, defined as at least 1 lesion with  $\geq 1$  cm in longest diameter, and  $\geq 2$  radiological tumour lesions in total. A maximum of 5 target lesions visible on CT/MRI will be defined, thereof not more than 2 lesions per organ (Eisenhauer et al., 2009)
6. Somatostatin receptor positive (SSTR+) disease, as evidenced by SSTR imaging (SRI) within 4 months prior to randomisation, as locally authorized, by:
  - $^{68}\text{Ga}$ -based SSTR PET imaging ( $^{68}\text{Ga}$ -edotreotide or  $^{68}\text{Ga}$ -DOTATATE), or
  - $^{111}\text{In}$ -pentetreotide SSTR SPECT/planar imaging, or
  - $^{99\text{m}}\text{Tc}$ -octreotide SSTR SPECT/planar imaging
  - $^{64}\text{Cu}$ -based SSTR PET imaging ( $^{64}\text{Cu}$ -DOTATATE) if approved according to local regulations

All target lesions and  $\geq 90\%$  of non-target lesions need to be positive for SSTR; this relates to lesions of at least 15 mm in diameter acquired on SRI images with SPECT, and of at least 10 mm in diameter acquired on SRI images with PET systems.

7. The patient must have progressive disease based on RECIST 1.1 Criteria as evidenced by two morphological imaging examinations made with the same imaging method (either CT or MRI), within a maximum of 36 months prior to randomisation. The most recent scan must not be older than 90 days prior to randomisation date. The minimum interval between the two scans must be  $\geq 90$  days.
8. Karnofsky performance status (KPS) scale  $\geq 70$  (see [Appendix 3](#))
9. Life expectancy allows the patient to participate in the study based on the investigator's assessment
10. Glomerular filtration rate (GFR, CKD-EPI)  $\geq 60\text{mL/min/1.73 m}^2$  (see Section [8.3.9](#))
11. For patients included in France only, verification and confirmation of their affiliation with a social security
12. Patients with functional P-NETs who require SSA for symptom control may continue SSA treatment throughout the study, on condition that:
  - a) they have been on a stable dose for at least three months prior to study enrollment

- b) that progressive disease has been diagnosed while under such stable dose

#### **4.2.2 Exclusion Criteria**

A patient will be excluded from participation in the trial if one or more of the following criteria are met:

1. Known hypersensitivity to edotreotide or everolimus or any other Rapamycin derivative
2. Known hypersensitivity to DOTA, lutetium-177, or any excipient of edotreotide or everolimus
3. Known hypersensitivity to lysine, arginine, or any excipient of the nephroprotective amino acid solution
4. Prior exposure to any peptide receptor radionuclide therapy (PRRT), including Lu-edotreotide, Y-edotreotide or other SSTR-targeting agents (e.g. Lu-octreotate or high-dose In-pentetreotide)
5. Prior therapy with mTOR inhibitors
6. Prior EFR (external field radiation) to GEP-NET lesions within 90 days before randomisation or radioembolisation therapy (e.g. Y microspheres, I-lipiodol) with administration to the liver
7. Prior therapy with chemotherapy, immunotherapy, interferon, chemo-embolisation, bland embolisation, cyclosporine-A within 4 weeks before randomisation; any new cancer treatment between screening and randomisation
8. Therapy with an investigational compound and/or medical device within 30 days or 5 half-life periods (whichever is longer) prior to randomisation
9. Subjects who have received a live vaccine up to 4 weeks prior to first dose
10. Current therapy with any prohibited medication (see Section [6.1.1](#))
11. Ongoing toxicity grade 2 from previous standard or investigational therapies (NCI-Common Terminology Criteria for Adverse Events [CTCAE] version 4.03)
12. Indication for surgical lesion removal with curative potential
13. Planned (for the period of study participation): chemotherapy, immunotherapy, radiation therapy, chemo-embolisation, bland embolisation, radio-embolisation, treatment with cyclosporine-A
14. Neuroendocrine tumours, not meeting the inclusion criteria:
  - With known non-GEP-NET origin (e.g. pulmonary or gonadal primaries)
  - Functional GE-NET
  - Explicit diagnosis of unknown primary (CUP)

- G3 neuroendocrine tumours and neuroendocrine carcinomas
  - NET for which no histological specimen for secondary histological analysis can be obtained
15. Total hepatic tumour burden >70%
16. Brain metastases
17. Other malignancy within previous 5 years (except basal cell carcinomas and in situ squamous cell carcinomas of the skin)
18. Serious non-malignant disease (e.g. psychiatric, infectious, autoimmune or metabolic), that may interfere with the objectives of the study or with the safety or compliance of the subject, as judged by the investigator
19. Clinically relevant renal, hepatic, cardiovascular, or haematological organ dysfunction, potentially interfering with the safety of the study treatments, as follows:
- Renal
    - Renal obstruction
  - Hepatic
    - Total bilirubin >1.5 x ULN
    - AST or ALT >2.5 x ULN
    - Alkaline phosphatase >5 x ULN
    - Albumin <3 g/dL, unless prothrombin time is within normal range
  - Cardiovascular
    - New York Heart Association classification III and IV
    - Uncontrolled hypertension
  - Haematopoietic
    - Platelets  $\leq 80 \times 10^9/L$
    - Absolute neutrophil count (ANC)  $< 1 \times 10^9$  cells/L
20. Pregnant (see Section 8.3.6) or breast-feeding women. Female patients of childbearing potential or male patients with female partners of childbearing potential, unless willing to practice full and true sexual abstinence or who are surgically/permanently sterile (bilateral tubal occlusion, hysterectomy, or vasectomy), or female patients whose male partners have medically successful vasectomy (provided the partner is the sole sexual partner of the female patient of childbearing potential), or who are not willing to practice highly effective contraception in combination with a barrier method of contraception (e.g. condom). Contraception methods that are considered highly effective are: oral or non-oral (injected or implanted) non-oestrogen progesterone-based hormonal method; oral, intravaginal, or

transdermal combined oestrogen and progesterone-based hormonal method; and/or intrauterine device (IUD), and/or intrauterine hormone-releasing system (IUS). Sexual abstinence or the contraception methods described above must be followed throughout the entire study period and for 56 days after treatment in the everolimus group and, 66 days in the PRRT group (10 half-lives of  $^{177}\text{Lu}$ ) after the last treatment cycle (see Section 8.3.1.1).

21. Subjects not able to declare meaningful informed consent on their own (e.g. with legal guardian for mental disorders) or any other vulnerable population to that sense (e.g. persons institutionalised, incarcerated etc.)

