--	--

Exclusion criteria	
A patient will be excluded from participation in the trial if one or more of the following criteria are met:
 
 
1. Known hypersensitivity to edotreotide or everolimus
 
2. Known hypersensitivity to DOTA, lutetium-177, or any excipient of edotreotide or everolimus or any other Rapamycin derivative
 
3. Known hypersensitivity to lysine, arginine, or any excipient of the nephroprotective amino acid solution
 
4. Prior exposure to any peptide receptor radionuclide therapy (PRRT), including Lu-edotreotide, Y-edotreotide or other SSTR-targeting agents (e.g. Lu-octreotate or high-dose In-pentetreotide)
 
5. Prior therapy with mTOR inhibitors
 
6. Prior EFR (external field radiation) to GEP-NET lesions within 90 days before randomisation or radioembolisation therapy (e.g. Y microspheres, I-lipiodol) with administration to the liver
 
7. Prior therapy with chemotherapy, immunotherapy, interferon, chemo-embolisation, bland embolisation, cyclosporine-A within 4 weeks before randomisation; any new cancer treatment between screening and randomisation
 
8. Therapy with an investigational compound and/or medical device within 30 days or 5 half-life periods (whichever is longer) prior to randomisation
 
9. Subjects who have received a live vaccine up to 4 weeks prior to first dose
 
10. Current therapy with any prohibited medication (see Section 6.1.1)
 
11. Ongoing toxicity grade 2 according to CTCAE version 4.03 from previous standard or investigational therapies
 
12. Indication for surgical lesion removal with curative potential
 
13. Planned (for the period of study participation): chemotherapy, immunotherapy, interferon, radiation therapy, chemo-embolisation, bland embolisation, radio-embolisation, treatment with cyclosporine-A
 
14. Neuroendocrine tumours, not meeting the inclusion criteria: 
 
• With known non-GEP-NET origin (e.g. pulmonary or gonadal primaries)
 
• Functional GE-NET
 
• Explicit diagnosis of unknown primary (CUP)
 
• G3 neuroendocrine tumours and neuroendocrine carcinomas
 
• NET for which no histological specimen for secondary histological analysis can be obtained
 
 
 
15. Total hepatic tumour burden >70%
 
16. Brain metastases
 
17. Other malignancy within previous 5 years (except basal cell carcinomas and in situ squamous cell carcinomas of the skin)
 

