#### **5.4.3.2 DMT during Lu-Edotreotide PRRT**

Dose modifying toxicity (DMT) during Lu-edotreotide treatment is defined as any of the following conditions which are ongoing on day 90 following the preceding PRRT cycle (i.e. at the time of the next scheduled PRRT cycle, as established during the respective pre-treatment evaluations):

- Grade 2 CTCAE or above toxicity for platelet count
- Grade 4 CTCAE lymphopenia
- Grade 3 CTCAE or above toxicity for any other haematological parameter
- 40% increase over baseline in serum creatinine
- decrease of over 40% in creatinine clearance from baseline
- any other Grade 4 CTCAE toxicity considered at least possibly related to study drug, regardless of duration, with the exception of liver enzymes (ASAT, ALAT, AP), which will not be used to define DMT.

Patients experiencing DMT from Lu-edotreotide treatment may receive subsequent PRRT cycles, provided that toxicity has subsided below the values defined above by week 16 following the non-tolerated PRRT administration.

With regard to renal DMT, further PRRT cycles may only be administered, if the following additional conditions are met by week 16:

- Serum creatinine level must be classified CTCAE Grade 0,
- Calculated creatinine clearance must have improved to within 20% from baseline (i.e. at least 80% of initial value)
- The GFR is at least  $\geq 50$  ml/min/1.73 m^2. A GFR value below 50 ml/min/1.73 m^2 will preclude further administration of Lu-edotreotide.

In patients with renal DMT, the eGFR (estimated GFR), needs to be confirmed by a non-radioactive plasma clearance method (e.g. 24 h creatine collection in urine), prior to administration of further administration of  $^{177}\text{Lu}$ -edotreotide, in all cases, where the eGFR is  $\geq 50 \text{ mL/min/1.73m}^2$  and  $\leq 60 \text{ mL/min/1.73m}^2$  at 16 weeks. In cases where eGFR is  $>60 \text{ mL/min/1.73m}^2$  at 16 weeks, no confirmation by a non-radioactive plasma clearance method is required.

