##### Pregnancy

Following the existing international guidelines on embryo-foetal Risk Mitigation and Risk Assessment of Medicinal and Investigational Medicinal Products on Human Reproduction and Lactation and in consideration with the absence of adequate data from the use of the reference study drug in pregnant women and its effects including known embryotoxicity and fetal toxicity as well as considering the known risks of radiation exposure to the embryo or foetus from therapeutic procedures with the administration of radioactive pharmaceuticals, highly effective contraceptive methods that can achieve a failure of less than 1% per year when used consistently and correctly are considered to be used in this study. Female patients of childbearing potential as well as male patients having female partners of childbearing potential, unless surgically/permanently sterile (bilateral tubal occlusion, hysterectomy, or vasectomy), will be excluded from participation in the study unless they are willing to: practice full and true sexual abstinence, or use highly effective contraception in combination with a barrier method of contraception (e.g. condom). Contraception methods that are considered highly effective are: oral or non-oral (injected or implanted) non-oestrogen progesterone-based hormonal

method; oral, intravaginal, or transdermal combined oestrogen and progesterone-based hormonal method; and/or IUD, and/or IUS. Sexual abstinence or the contraception methods described above must be followed throughout the entire study period and for 56 days after treatment in the everolimus group and 66 days in the PRRT group (10 half-lives of  $^{177}\text{Lu}$ ) after the last treatment cycle. True abstinence may be practised if this is in line with the preferred and usual lifestyle of the subject. Periodic abstinence (e.g. calendar, ovulation, symptothermal, post-ovulation methods), declaration of abstinence for the duration of exposure to IMP, and withdrawal are *not* acceptable methods of contraception. A partner who has a medically successful vasectomy is a highly effective birth control method provided the partner is the sole sexual partner of the female patient of childbearing potential.

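### Exclusion criteria 11 and 20 do not work as written: one names a single toxicity grade, the other lists unwillingness to use contraception among its exceptions

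*Protocol*

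**What the plan says.** Protocol Section 4.2.2 opens with the rule that gives each item its force: "A patient will be excluded from participation in the trial if one or more of the following criteria are met". An item that is not met does not exclude.

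**Criterion 11.** The body text reads "Ongoing toxicity grade 2 from previous standard or investigational therapies". The synopsis reads "Ongoing toxicity grade 2 according to CTCAE version 4.03 from previous standard or investigational therapies". Neither carries a comparison sign or words that turn the grade into a floor. Section 5.4.3.2, which defines dose-modifying toxicity during PRRT, does state a floor where it wants one: "Grade 2 CTCAE or above toxicity for platelet count". It does the same, at grade 3, for haematological parameters other than platelets and lymphocytes.

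**Criterion 20.** Patients of childbearing potential, and men with such partners, are excluded "unless willing to practice full and true sexual abstinence or who are surgically/permanently sterile". The list of exceptions goes on to women with a vasectomised partner and ends with those "or who are not willing to practice highly effective contraception in combination with a barrier method of contraception". The synopsis has the same clause. The criterion closes by making abstinence or contraception compulsory during the study and for a set period afterwards. The body version then points to Section 8.3.1.1, where such patients, unless sterile, "will be excluded from participation in the study unless they are willing to: practice full and true sexual abstinence, or use highly effective contraception".

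The SAP does not restate eligibility; its Section 3.2 refers back to Protocol Section 4.2.

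**The concern.** An exclusion criterion should catch at least the patients at higher risk on the dimension it names. Taken literally, criterion 11 excludes a patient with ongoing grade 2 toxicity and passes over one with ongoing grade 3 or 4. Taken literally, criterion 20 exempts the patient who refuses contraception and exempts no one on the ground of agreeing to it.

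Both are safety rules. Section 8.3.1.1 bases the contraception requirement on known embryotoxicity of the reference drug and on radiation risk to the foetus. Prior-therapy toxicity concerns mainly second-line patients, one of the two levels of a stratification factor. Section 3.5 demands strict adherence to the protocol as specified, and Section 12.1 asks that its instructions be followed exactly. About 60 centres in 10 to 15 countries apply these sentences. A centre that silently corrects the text and one that reads it literally could reach different decisions on the same patient.

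**Working it through.** No arithmetic applies. The check sets the passages side by side.

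**Step 1. Is the single grade in criterion 11 a slip of one copy, or of the PDF reading?** The synopsis and body are worded slightly differently, yet both name grade 2 alone. A lost sign would have to vanish in both, while signs survive in neighbouring criteria (hepatic burden >70% in criterion 15, AST or ALT >2.5 x ULN in criterion 19). A lost sign cannot be fully ruled out but is unlikely.

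**Step 2. Which ongoing grade 3-4 toxicity is caught elsewhere?** Criterion 19 covers "Clinically relevant renal, hepatic, cardiovascular, or haematological organ dysfunction, potentially interfering with the safety of the study treatments", but only through the limits it then lists.

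| Toxicity | Entry limit outside criterion 11 | Rule for later PRRT cycles |
|---|---|---|
| Platelets | Criterion 19: excluded at ≤80 x 10^9/L. Appendix 4 puts grade 3-4 at <50, so it is caught | 5.4.1.2 and 5.4.3.2 |
| Neutrophils | Criterion 19: excluded at <1 x 10^9/L. Appendix 4 puts grade 3-4 at <1, so it is caught | 5.4.3.2, grade 3 or higher |
| Liver values | Criterion 19: bilirubin, AST/ALT, alkaline phosphatase, albumin | 5.4.1.2: bilirubin, albumin |
| Kidney | GFR ≥60 (inclusion 10); renal obstruction (criterion 19) | 5.4.1.2 and 5.4.3.2 |
| Cardiovascular | Criterion 19: NYHA III-IV, uncontrolled hypertension | none specific |
| Haemoglobin | none | 5.4.1.2: ≥8.0 g/dL; 5.4.3.2: grade 3 or higher |
| Total white cells | none | 5.4.1.2: ≥2 x 10^9/L; 5.4.3.2: grade 3 or higher |
| Lymphocytes | none | 5.4.3.2: grade 4 |
| Most non-laboratory toxicity (e.g. neuropathy, diarrhoea) | KPS ≥70; investigator judgement under criterion 18 | 5.4.3.2: only grade 4 and at least possibly related to study drug |

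The gap is therefore the last four rows. For the three blood counts the protocol is also out of step with itself. A patient could enter with a value that Section 5.4.1.2 or 5.4.3.2 uses to withhold or delay a later cycle, and the haematological items in 5.4.3.2 do not depend on attribution to study drug.

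**Step 3. Can criterion 20 be parsed so that it works?** Take a patient of childbearing potential who is neither abstinent nor sterile and has no vasectomised partner.

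| Reading of the last clause | Refuses contraception | Agrees to contraception |
|---|---|---|
| One more exception after *unless* | not excluded | excluded |
| A further excluded group | excluded | excluded |
| Section 8.3.1.1 | excluded | not excluded |

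Neither reading of the sentence gives the result in Section 8.3.1.1. The first reverses it; the second shuts out willing contraceptive users.

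**The case against.** The strongest reply is that the intent is plain and the protocol guards it elsewhere. For criterion 20 this largely stands. Its closing sentence makes abstinence or contraception compulsory, Section 8.3.1.1 states the rule correctly, Section 8.3.6 requires monthly pregnancy tests, and Sections 4.4.1 and 8.3.6 stop study treatment on pregnancy. A reader might infer that patients who refuse contraception will be enrolled. The documents do not support that, because such a patient could not comply with the criterion's own last sentence. What stands is a contradiction inside an operative entry rule.

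For criterion 11, a reader might infer that all ongoing grade 3-4 toxicity can enter. It cannot. Criterion 19, the GFR and KPS limits and criterion 18 catch part of it. Criterion 7 adds a four-week gap after chemotherapy, immunotherapy, interferon and embolisation. Criterion 5 bars prior mTOR inhibitors, so their toxicity cannot be carried in.

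A reader might also infer that grade 3 neuropathy or diarrhoea left by earlier treatment would stop PRRT dosing. Section 5.4.3.2 does not say so: outside the haematological and renal items it requires grade 4 and a possible link to study drug. Nor do the documents show how sites record eligibility. The eCRF is not among them, and Section 7.2.1 says only that the number of the unmet criterion is recorded for screen failures.

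Finally, it is fair to say that the synopsis and body agree on criterion 11, and that Section 5.4.3.2 uses different grades for different toxicities. The documents therefore do not settle which grades were meant.

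**Conclusion.** Both criteria are wrong as written, and the consequence is limited. Criterion 11 names one grade where the protocol's usage elsewhere suggests that a range was meant. Its literal reading leaves ongoing grade 3-4 toxicity uncovered for haemoglobin, total white cells, lymphocytes and most non-laboratory toxicity, apart from KPS and investigator judgement. Criterion 20 is inverted and contradicts Section 8.3.1.1 and its own closing sentence, although the intended rule can be recovered from them.

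The number of patients affected cannot be estimated, because the documents give no counts. Nothing in the estimand, sample size, alpha or analysis depends on it. It should still be corrected: these are safety-related entry rules in a protocol that demands strict adherence, and the correction is cheap. The conclusion assumes that no comparison sign was lost from criterion 11 in both places. If one was, that half of the point falls and the half on criterion 20 remains.

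**What to change.** For criterion 11, the sponsor should state explicitly, in the synopsis and in Section 4.2.2, which grades are excluded. It should reconcile the wording with the threshold style of Section 5.4.3.2 and with the continuation criteria in Section 5.4.1.2, including whether the absence of any entry limit for haemoglobin, total white cells and lymphocytes is intended. The choice of grades is a clinical matter for the sponsor, and none is proposed here.

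For criterion 20, the sponsor should reconcile the sentence in both places with Section 8.3.1.1, so that all three passages give the same result for willing and unwilling patients, and keep the provision for a vasectomised partner. Redrafting the whole sentence is cleaner than adding a second *unless* to it. Any site eligibility checklist that repeats these criteria should follow the corrected text.

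The cost is two sentences, each in two places, in an amendment. If the sponsor's clarification of criterion 11 brings in higher grades, a few patients may have to wait for recovery before entry or may not enter. No analysis changes.
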